**Table 7.4.1-2: Administration of study therapy: definition of parameters, PO therapies in Randomized Phase**

	Anastrozole	Abemaciclib	Palbociclib
Dosing schedule per protocol	1 mg QD	150 a mg BID	125 b mg QD × 3 weeks on and 1 week off

**Table 7.4.1-2: Administration of study therapy: definition of parameters, PO therapies in Randomized Phase**

	Anastrozole	Abemaciclib	Palbociclib
Dose	Dose (mg) is defined as Total Dose administered (mg). Dose administered in mg at each dosing date and weight are collected on the CRF.	Dose (mg) is defined as Total Dose administered (mg). Dose administered in mg at each dosing date and weight are collected on the CRF.	Dose (mg) is defined as Total Dose administered (mg). Dose administered in mg at each dosing date and weight are collected on the CRF.
Cumulative dose	Cum dose (mg) is sum of the doses (mg) administered to a subject during the treatment period.	Cum dose (mg) is sum of the doses (mg) administered to a subject during the treatment period.	Cum dose (mg) is sum of the doses (mg) administered to a subject during the treatment period.
Average daily dose (actual)	Cumulative dose in mg / duration of treatment in days	Cumulative dose in mg / duration of treatment in days	Cumulative dose in mg / duration of treatment in days
Average daily dose (planned)	1 mg	300 c mg	93.75 d mg (125 mg × 21 days / 28 days)
Relative dose intensity (%)	(Actual average daily dose / planned average daily dose) × 100	(Actual average daily dose / planned average daily dose) × 100	(Actual average daily dose / planned average daily dose) × 100
Duration of treatment	Last dose date - Start dose date +1	Last dose date - Start dose date +1	Last dose date - Start dose date +8

a Scheduled dose of abemaciclib could be 150 mg, 100 mg or 50 mg BID depending on the dose cohort in safety run-in phase and the recommended phase 2 dose (RP2D) identified from safety run-in phase which is applied in randomized phase.

b Scheduled dose of palbociclib could be 125 mg, 100 mg or 75 mg QD × 3 weeks on (1 week off) depending on the dose cohort in safety run-in phase and RP2D in randomized phase.

c Planned average daily dose of abemaciclib could be 300 mg, 200 mg or 100 mg depending on the dose cohort in safety run-in phase and RP2D in randomized phase.

d Planned average daily dose of palbociclib could be 93.75 mg, 75 mg or 56.25 mg depending on the dose cohort in safety run-in phase and RP2D in randomized phase.

### 7.4.2 Modifications of Study Therapy

Participants are to start nivolumab within 3 calendar days of randomization. Participants will receive nivolumab at a dose of 480 mg as a 30-minute IV infusion for a maximum of 5 cycles (maximum 4 cycles for Arm B). Doses of nivolumab may be interrupted, omitted, or discontinued, depending on how well the participant tolerates the treatment. There will be no dose escalations or reductions of nivolumab allowed. For Q4W dosing cycles, participants may be dosed within a ± 3-day window. If a participant cannot receive nivolumab within a ± 3-day window, nivolumab must be omitted (skipped) for that cycle. If nivolumab is omitted, the other study medications may continue. If a participant discontinues nivolumab, the entire study treatment (CDK4/6 inhibitor

and anastrozole) must be discontinued. When nivolumab is scheduled to be administered on the same day with palbociclib plus anastrozole, nivolumab dosing should be started > 1 hour after palbociclib plus anastrozole ingestion. If nivolumab cannot be given within 3 days of palbociclib plus anastrozole administration for a given cycle, nivolumab must be omitted for that cycle. Participants who require a dose omission for nivolumab should be re-evaluated and resume treatment at the next cycle when re-treatment criteria are met.

Palbociclib can be interrupted, reduced, or discontinued both within a cycle and between cycles.

No dose modification for anastrozole is listed per full prescribing information.

Dose escalations (within subject) are not permitted for any study drugs.

Reason for dose modification will be retrieved from CRF dosing pages.

- The following parameters will be summarized by treatment group:
- Number of subjects with at least one dose modification (interrupted nivolumab dose, omitted nivolumab dose, interrupted palbociclib dose, reduced palbociclib dose).
- Number of nivolumab and/or palbociclib dose modifications per subject.
- Reason of nivolumab and/or palbociclib dose modification.

#### **7.4.2.1 Infusion Interruptions and Rate Changes**

Each nivolumab infusion can be interrupted and/or the IV infusion rate can be reduced. This information will be retrieved from CRF dosing pages.

- The following parameters will be summarized by treatment group:
- Number of subjects with at least one dose infusion interruption, the reason for interruption, and the number of infusion interruptions per subject.
- Number of subjects with at least one IV infusion rate reduction, the reason for reduction and the number of infusions with IV rate reduction per subject.

#### **7.4.3 Concomitant Medications**

Concomitant medications, defined as medications other than study medications which are taken at any time on-treatment (i.e. on or after the first day of study therapy and within 100 days following the last dose of nivolumab in Arm A, B and Safety Run-in cohorts; on or after the first day of study therapy and within 30 days following the last dose of study treatment in Arm C), will be coded using the UMC WHO Drug Global Dictionary. Anastrozole administered after completion of 5 cycles of neoadjuvant treatment (or EOT) up to subsequent breast surgery must be collected as concomitant medication.

The following summary table will be provided:

- Concomitant medications (subjects with any concomitant medication, subjects by medication class and generic term)

A by-subject listing(s) will accompany the table(s).

### **7.4.3.1 Immune modulating medication**

Immune modulating concomitant medications are medications entered on an immune modulating medication form or available from the most current pre-defined list of immune modulating medications. The list of anatomic class, therapeutic class and generic name used for the selection at the time of the database lock will be provided.

The percentage of subjects who received immune modulating concomitant medication for

- management of adverse event
- premedication
- other use
- any use
- management of drug-related select adverse event (any grade, grade 3-5) by select AE category/subcategory (EU/ROW Submissions)
- management of IMAEs (any grade, grade 3-5) by IMAE category (US Submission)

will be reported separately for each treatment group (percentages of treated subjects by medication class and generic term).

For each category/subcategory of drug-related select AEs (any grade, grade 3-5) and IMAEs (any grade, grade 3-5), the following will be reported for each treatment group:

- The total immune modulating medication treatment duration (excluding overlaps), duration of high dose of corticosteroid, initial dose of corticosteroid, and tapering duration (summary statistics)

Duration represents the total duration the subject received the concomitant medication of interest. If the subject took the medication periodically, then DURATION in the summation of all use. Initial dose represents the dose of the concomitant medication of interest received at the start of the event. In the case multiple medications started on the same date, the highest equivalent dose is chosen and converted to mg/kg by dividing by the subject's recent weight.

These analyses, except the ones related to IMAEs will be conducted using the 30-day safety window. The analyses related to IMAEs will be conducted using the 100-day safety window.

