- Grade 2 uveitis, episcleritis, iritis, eye pain, or blurred vision that does not respond to topical therapy and does not improve to Grade 1 severity within 2 weeks OR requires systemic treatment.
- Grade ≥ 3 electrolyte abnormality associated with clinical symptoms.
- Grade 3 fatigue lasting ≥ 1 week.
- Other Grade 3 \geq toxicity will be considered a DLT, except those clearly and incontrovertibly due to disease progression and extraneous causes. However, the following Grade 3 or 4 events will not be considered DLTs:
 - Isolated Grade 3 or 4 electrolyte imbalances/abnormalities not associated with clinical symptoms and either resolve spontaneously or are corrected with supplementation/appropriate management within 72 hours of their onset. Confirmatory laboratory test is required within 72 hours.
 - Grade ≥ 3 amylase or lipase elevation not associated with symptoms or clinical manifestations of pancreatitis.
 - Grade 3 nausea or vomiting that lasts less than 48 hours and either resolves spontaneously or responds to medical intervention.
 - Grade 3 fever not associated with hemodynamic compromise (eg, hypotension, clinical or laboratory evidence of impaired end-organ perfusion).
 - Grade 3 endocrinopathy that is well controlled by hormone replacement.
 - Grade 3 tumor flare (defined as pain, irritation, or rash that localizes to sites of known or suspected tumor).

5.1.2.2 **Randomized Phase**

The Randomized Phase will start after the combinations tested in the Safety Run-in Phase are confirmed to be safe by BMS in collaboration with Investigators, and the appropriate dose level communicated to Investigators. Following confirmation of eligibility criteria, participants will be randomized to either Arm A, Arm B, or Arm C in a 4:4:3 ratio, respectively. Participant randomization will be stratified using the following factors:

- 2) Evaluation of lymph nodes (cytologically positive vs radiologically or cytologically negative), and
- 3) Tumor size (> 3 cm or ≤ 3 cm).

Treatment must begin within 3 calendar days following randomization.

Participants will be randomly assigned to 1 of the 3 treatment arms below:

As of Revised Protocol 03, the abemaciclib-containing combination arms have been removed from the randomization phase of the study.

- 1) Arm A (concurrent palbociclib treatment arm): nivolumab 480 mg Q4W IV + palbociclib 125 mg QD PO for 3 weeks (1 week off) + anastrozole 1 mg QD PO for 5 cycles
- 2) Arm B (phased palbociclib treatment arm):

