7.7.4 Permitted Therapy

Participants are permitted the use of topical, ocular, intra-articular, intranasal, and inhalational corticosteroids (with minimal systemic absorption). A brief (less than 3 weeks) course of corticosteroids for prophylaxis (eg, contrast dye allergy) or for treatment of non-autoimmune conditions (eg, delayed-type hypersensitivity reaction caused by a contact allergen) is permitted.

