#### **7.6.7.3 Time-to Resolution of Select AE**

Time-to resolution of the following specific events will be summarized separately for each category/subcategory.

- Time-to resolution of drug-related select AE (any grade, grade 3-5) by treatment group.
- Time-to resolution of drug-related select AE (any grade, grade 3-5) where immune modulating medication was initiated, by treatment group.

Time-to resolution analyses are restricted to treated subjects who experienced the specific events. Time-to resolution where immune modulating medication was initiated analyses are restricted to treated subjects who experienced the specific events and who received immune modulating medication during the longest select AE.

The analyses will be conducted using the 30-day safety window.

The following summary statistics will be reported: percentage of subjects with resolution of the longest select AE, median time-to resolution along with 95% CI (derived from Kaplan-Meier estimation) and ranges.

See time-to resolution definition subsection of [APPENDIX 1](#) for additional details.

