### **Time-to resolution definition**

In order to derive the time-to resolution, overlapping or contiguous AEs within a specific category or subcategory will be collapsed into what will be termed “clustered” AEs. For example, if a subject (without pre-treatment AE) experienced an AE from 1st to 5th January, another AE (with different PT but within same category) from 6th to 11th January and same AE from 10th to 12th January, these will be collapsed into one clustered AE from 1st to 12th January. [Table 8-1](#) is summarizing key derivation steps for each type of clustered AEs.

Time-to resolution of AE (any grade) for a specific category is defined as the longest time from onset to complete resolution or improvement to the grade at baseline among all clustered AEs experienced by the subject in this category per adverse event criteria category. Events which worsened into grade 5 events (death) or have a resolution date equal to the date of death are considered unresolved. If a clustered AE is considered as unresolved, the resolution date will be censored to the last known alive date. Improvement to the grade at baseline implies that all different events in the clustered adverse event should at least have improved to the corresponding (i.e. with same preferred term) baseline grade. This measure is defined only for subjects who experienced at least one AE in the specific category.

The time-to resolution of AE (grade 3-5) for a specific category is defined similarly with an onset date corresponding to a grade 3-5 AE.

Time-to resolution of drug-related AE (any grade or grade 3-5) for a specific category is defined similarly but restricted to drug-related AE.

The time-to resolution of AE (any grade or grade 3-5, drug-related or all) where immune modulating medication was initiated is defined similarly. For data presentation not restricted to IMAE, the additional condition that the subject started an immune modulating medication during the longest AE resolution period will be applied.

Time-to resolution for a specific subcategory is defined similarly but restricted to event of this subcategory.

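### The initial corticosteroid dose is anchored to adverse event onset, so it is undefined or unrelated whenever the treating steroid starts later

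*SAP*

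**What the plan says.** SAP 7.4.3.1 describes the immune modulating medication given for each category or subcategory of drug-related select adverse event and for each category of immune-mediated adverse event (IMAE). It does so for any grade and for grade 3-5, by treatment group. The corticosteroid variables are the "duration of high dose of corticosteroid, initial dose of corticosteroid, and tapering duration (summary statistics").

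The initial dose is then defined: "Initial dose represents the dose of the concomitant medication of interest received at the start of the event". The following sentence deals with ties: "In the case multiple medications started on the same date, the highest equivalent dose is chosen and converted to mg/kg", using the participant's recent weight.

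Two other places describe when the medication may start. SAP 7.6.7.3 restricts one time-to-resolution analysis to participants "who received immune modulating medication during the longest select AE". SAP Appendix 1 adds, for presentations not restricted to IMAEs, "the additional condition that the subject started an immune modulating medication during the longest AE resolution period will be applied".

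**The concern.** An initial steroid dose is normally the first dose given to treat the event. The SAP instead takes the dose on the day the event begins. The two agree only when treatment starts on the onset day. The SAP's own wording elsewhere does not require that, and nothing else in the two documents moves the anchor.

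At stake is a summary of how immune toxicity was treated. Safety and tolerability are a secondary objective, and the planned arms are small (40, 40 and 30 participants). A category may therefore hold few treated events, and one missing or misattributed dose could visibly change its summary.

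**Working it through.** The point concerns a definition, so there is no plan figure to reproduce and no formula to apply. The check is to follow the wording through each possible order of events.

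**Inputs**
- Anchor as written: start of the event (SAP 7.4.3.1).
- Permitted start of immune modulating medication: any time during the event or its resolution period (SAP 7.6.7.3, Appendix 1).
- Delayed systemic treatment is foreseen in at least one setting. The ocular criterion in Protocol 5.1.2.1 covers a Grade 2 event "that does not respond to topical therapy and does not improve to Grade 1 severity within 2 weeks OR requires systemic treatment".
- A steroid in use at onset need not be for the event. Protocol 7.7.4 permits "A brief (less than 3 weeks) course of corticosteroids for prophylaxis (eg, contrast dye allergy"). Protocol 7.4.4.3 allows corticosteroid premedication for infusions after a Grade 2 infusion reaction. Protocol 7.7.2 allows physiological replacement. Protocol 7.4.4.2 and 8.1.1 describe long tapers that could run into a later event. SAP 7.4.3.1 itself lists premedication and other use separately from management of an adverse event.

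**Cases under the literal rule**

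| Steroid for the event starts | Other steroid in use at onset | Value returned |
|---|---|---|
| On the onset day | No | First treating dose: correct |
| After onset | No | No dose exists: missing, or zero if so coded |
| After onset | Yes | The other steroid's dose: unrelated |

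If the anchor is the first corticosteroid record for management of the event, on or after onset, all three rows return the first treating dose.

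**An IMAE consequence.** Under SAP 7.1.1.3 a non-endocrine event counts as an IMAE only if it was treated with immune modulating medication. Where that medication is a corticosteroid, a first treating dose exists. The literal rule still returns nothing if treatment began after onset and no other steroid was in use.

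**Clusters.** SAP Appendix 1 collapses contiguous or overlapping records in a category. Its own example merges records of 1-5, 6-11 and 10-12 January into one event running from 1 to 12 January. Suppose, as an illustration, that a steroid is started for the second record on 6 January. If the event is the cluster, its start is 1 January, 5 days before any dose. If the event is the individual record, the dose is captured. SAP 7.4.3.1 does not say which is meant. Table 8-1 bases grade 3-5 resolution on the onset of the earliest grade 3-5 record, but 7.4.3.1 does not say whether the dose follows that date.

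**The case against.** The strongest reply is that the tie-break sentence chooses among medications by the date they started. That suggests the authors had the steroid start date in mind, and a programmer summarising an initial dose for treated events would probably take the first treating record. This would make the issue a drafting slip. Much of that is fair. However, the tie-break only selects among medications that start on the same day and does not reset the anchor. The result is two adjacent sentences that point to different dates.

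The SAP also refers to an IO Core SAP for safety detail and to a non-study medication specification. Neither is available here, so an operational rule may exist elsewhere. The present text does not point to one for this variable.

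The unrelated-dose case is narrowed by the protocol. Chronic steroids above replacement dose are an exclusion (6.2), and supraphysiological systemic doses are prohibited on study unless used to treat a drug-related adverse event (7.7.1). The exceptions listed above remain, so the case is possible but limited.

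Finally, the planned by-subject listings of concomitant medications, of adverse events requiring immune modulating medication and of IMAEs would let a reader check individual cases. They would not correct the summary table.

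**Conclusion.** The written rule is wrong for any event whose steroid starts after onset, and it conflicts with the sentence that follows it. The conclusion rests on a literal reading of 7.4.3.1 and on the absence of any overriding definition in the two documents. The effect is limited to one descriptive safety summary. The primary endpoints, the sample size and the confidence intervals for efficacy are untouched, and the dose-selection outputs listed in SAP 7.10 do not include this variable.

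Three stronger readings are tempting but not supported:
- **Frequency.** A reader might infer that most treated events are affected. Starting during an event includes starting on its first day, and neither document gives a lag from onset to treatment, so no proportion can be derived.
- **Direction of bias.** A reader might infer that captured doses would come mainly from more severe events. Nothing in the documents links severity to same-day treatment.
- **Duration.** A reader might extend the criticism to the duration rule: "Duration represents the total duration the subject received the concomitant medication of interest". The sentence after it, on adding up all use, concerns periodic use of that medication. It sits within a summary made by category, in a section that already attributes medication to management of events by category. The documents do not show that courses for other purposes would be counted.

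**What to change.** Replace the definition in SAP 7.4.3.1 with wording to this effect: the initial dose is the equivalent dose, in mg/kg, of the first corticosteroid record for management of an event in that category, dated on or after the onset of the event; if several corticosteroids start on that date, the highest equivalent dose is used. Add one sentence stating whether onset means that of the individual record or of the cluster, and which onset applies in the grade 3-5 summaries.

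The cost is two sentences of SAP text and the matching programming specification. No new data should be needed. The section already plans to report immune modulating medication for management of events by category, which requires the link between medication and category, and the tie-break already relies on medication start dates.

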### **7.4.3.2 Subsequent Cancer Therapy**

Number and percentage of subjects receiving subsequent cancer therapies will be summarized for all treated subjects (in safety run-in period) and all randomized subjects (in randomized phase). Categories include:

- Subsequent systemic therapy
- Subsequent surgery for treatment of tumors
- Subsequent radiotherapy for treatment of tumors

A by-subject listing of subsequent therapies will also be produced.

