Dispense Anastrozole 1 mg and Provide and Review Patient Diary (Safety Run-in Cohorts and all Arms)	X					To be administered QD PO, with or without food. Review patient diary at each study visit. Note: Anastrozole given beyond C5 or beyond EOT will not be considered as study treatment and must be collected as concomitant medication.
AND						
Dispense Abemaciclib and Provide/Review Patient Diary (Safety Run-in Cohort 1) ^e	X					To be administered BID PO with or without food. Review patient diary at each study visit.
OR						
Dispense Palbociclib and Provide/Review Patient Diary (Safety Run-in Cohort 2 and Arms A, B, and C)	X					To be administered QD PO with food during the first 3 weeks of each cycle (1 week off). Review patient diary at each study visit.

Abbreviations: AE = adverse event; BC = breast cancer; BCS = breast-conserving surgery; BID = twice daily; BP = blood pressure; C = cycle; CBC = complete blood count; D = day; ECG = electrocardiogram; ECOG = Eastern Cooperative Oncology Group; eCRF = electronic case report form; EOT = end of treatment; HR = heart rate; IRT = interactive response technology; IV = intravenous; mg = milligram; PE = physical examination; PO = per os, (by mouth); PS = performance status; QD = daily; Q4W = every 4 weeks; SAE = serious adverse event.

[figure not shown]
- a The schedule for each procedure should coincide with actual dosing.
 - b Participants will undergo surgical treatment within 4 weeks of the last dose of neoadjuvant treatment (IV or oral, whichever comes later).
 - c On-treatment procedures may generally be performed within a ± 3 -day window, unless otherwise specified (eg, breast ultrasound or mammogram, tumor biopsy).
 - d Some of the assessments referred to in this section may not be captured as data in the eCRF. They are intended to be used as safety monitoring by the treating physician. Additional testing or assessments may be performed as clinically necessary or where required by institutional or local regulations.
- 

Table 2-3: Follow-up Procedural Outline (Safety Run-in Phase and Randomized Phase; CA2097A8)

Procedure	30-Day Safety Follow Up (FU1) ^a (± 7 days) (All Participants in the Safety Run-in Phase and the Randomized Phase)	100-Day Safety Follow Up (FU2) ^a (± 7 days) (All Participants in the Safety Run-in Phase and Arms A and B Only in the Randomized Phase)	Notes ^b
Safety Assessments			

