[figure not shown]
In the Randomized Phase, participants will be randomly assigned by an IRT system to 3 different treatment arms and stratified by the following factors:

2) evaluation of lymph nodes (cytologically positive vs radiologically or cytologically negative); and 3) tumor size (> 3 cm or ≤ 3 cm).

For both the Safety Run-in Phase and Randomized Phase, participants will be treated for a maximum of 5 cycles (1 cycle = 4 weeks). Participants with progressive disease prior to completion of the 5-cycle study treatment must discontinue all study drugs and proceed to the Safety Follow-up Period. Participants who permanently discontinue the study drugs for any reason are considered to have completed the On-treatment Pre-surgery (neoadjuvant) Period, and hence reach end of treatment (EOT). After Cycle 5 or EOT, participants must continue to receive anastrozole (as concomitant medication and not as study treatment) until subsequent SOC breast surgery. Following the completion of neoadjuvant treatment, all participants who remain operative candidates will undergo definitive surgery for BC within 4 weeks of the last neoadjuvant treatment administration. If anastrozole can no longer be administered after EOT, participants will go to breast surgery right away. Pre-surgical lymph node biopsy is not allowed. Information on the type of the surgery will be collected and recorded in the electronic case report form (eCRF). Surgical specimens will be collected for the analyses outlined in the protocol. Depending on treatment assignment, up to 2 safety follow-up visits will be conducted in person. The first safety follow-up visit (FU1) will be completed for all participants within 30 days (± 7 days) from the last study treatment (oral or intravenous [IV], whichever occurs later). The second safety follow-up visit (FU2) will occur approximately within 100 days (± 7 days) from the last dose of nivolumab and will be required for participants in the Safety Run-in Phase and participants randomized to Arms A or B in the Randomized Phase. Further planned treatment of participants in the adjuvant setting (ie, radiotherapy, endocrine treatment, chemotherapy or any other treatment modality) will be at the discretion of the treating physician, following local clinical guidelines, and collected in the appropriate eCRF.

The study design schematic is presented in [Figure 5.1-1](#).

Figure 5.1-1: Study Design Schematic

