7.7 Concomitant Therapy

Concomitant medications, all forms of premedications, and supportive care are recorded at baseline and throughout study treatment and safety follow-up in the appropriate section of the eCRF at each visit.

All medications (prescription and over-the-counter), vitamin and mineral supplements, and/or herbs taken by the participant from Screening through the Safety Follow-up Period will be documented and recorded, including start and stop date, dose and route of administration, frequency, and indication. Medications taken for a procedure (eg, biopsy) should also be included.

Anastrozole administered after completion of 5 cycles of neoadjuvant treatment (or EOT) up to subsequent breast surgery must be collected as concomitant medication.

Any subsequent anti-cancer therapy (ie, adjuvant treatment, radiotherapy) will be recorded up to 100 days after last dose of nivolumab or 30 days after last dose of study treatment (Arm C), in the appropriate section of the eCRF.

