## 7.4 Extent of Exposure

Listings will include all available exposure data. Analyses will be performed by treatment group “as treated” in all treated subjects, unless otherwise specified.

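### Subsequent cancer therapy is collected for a shorter time in Arm C than in Arms A and B, but is tabulated as crude percentages with no common window

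*SAP*

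**What the plan says.** **Collection.** Protocol 7.7 says that later anti-cancer therapy "will be recorded up to 100 days after last dose of nivolumab or 30 days after last dose of study treatment (Arm C". In Protocol Table 2-3, new surgery, radiotherapy and systemic therapy are recorded at each follow-up visit. The 30-day visit (FU1) applies to everyone. The 100-day visit (FU2) applies to: "All Participants in the Safety Run-in Phase and Arms A and B Only in the Randomized Phase".

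**Subsequent-therapy table.** SAP 7.4.3.2 plans: "Number and percentage of subjects receiving subsequent cancer therapies will be summarized for all treated subjects (in safety run-in period) and all randomized subjects". Its categories are systemic therapy, surgery and radiotherapy. It gives no cut-off, censoring rule or adjustment for observation time. It does not itself mention arms; the grouping comes from the opening of SAP 7.4: "Analyses will be performed by treatment group".

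**Concomitant-medication table.** SAP 7.4.3 builds the unequal windows into its definition: "within 100 days following the last dose of nivolumab in Arm A, B and Safety Run-in cohorts", but "within 30 days following the last dose of study treatment in Arm C". One summary table is planned.

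**Timing of surgery.** Protocol 5.1 states: "all participants who remain operative candidates will undergo definitive surgery for BC within 4 weeks of the last neoadjuvant treatment administration". Adjuvant treatment afterwards is left to the treating physician.

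**The concern.** The extra collection time in Arms A and B falls in the weeks after surgery, when adjuvant treatment can be expected to begin. A crude percentage counts a participant only if therapy starts before collection closes. With identical true use in all three arms, the arms observed longer would tend to show the higher percentage.

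What is at stake is how a descriptive table is read. Arm C is labelled the control, so readers will look across the columns. They could take a difference produced by the data-collection schedule as something nivolumab did.

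Elsewhere the SAP deals with this problem. It names 30- or 100-day windows for most adverse-event tables (SAP 7.6.3 to 7.6.10), and its multiple-event analysis divides by arm-specific exposure time (SAP 7.1.1). SAP 7.4.3.2 has no equivalent rule.

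**Working it through.** The plan states no figure on this point to reproduce. The check is calendar arithmetic on its own windows, followed by an illustration under stated assumptions.

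**Inputs from the documents.** Five 28-day cycles (Protocol 5.1); nivolumab on Day 1 of each cycle, the last planned dose being in Cycle 5 in both Arm A and Arm B (Table 7.1-2); daily anastrozole as study treatment to the end of Cycle 5; surgery up to 28 days after the last dose; the collection limits above.

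**Step 1: end of collection, on-schedule completer.**
- Last nivolumab: 4 × 28 + 1 = Day 113. Last anastrozole as study treatment: 5 × 28 = Day 140.
- Arms A and B: 113 + 100 = Day 213. Arm C: 140 + 30 = Day 170. Gap: 213 − 170 = 43 days.
- If the last dose is instead taken as palbociclib on Day 21 of Cycle 5 (Day 133), Arm C closes on Day 163 and the gap is 50 days.

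**Step 2: observation after surgery.** With surgery s days after Day 140, Arms A and B have 73 − s days and Arm C has 30 − s days.

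| s | Arms A and B | Arm C |
|---|---|---|
| 0 | 73 | 30 |
| 14 | 59 | 16 |
| 28 | 45 | 2 |

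**Step 3: share of later therapy captured when true use is the same in every arm.** Assumptions, not from the documents: surgery is uniform over 7-28 days after last dose, and adjuvant start is uniform over the interval shown. Therapy is captured if the two times sum to at most 73 days (Arms A and B) or 30 days (Arm C). The shares are areas within the rectangle of possible times.

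| Start after surgery | Arms A and B | Arm C |
|---|---|---|
| 0-14 days | 100% (latest sum 42) | 1 − (12²/2)/(21 × 14) = 76% |
| 14-42 days | 100% (latest sum 70) | (9²/2)/(21 × 28) = 7% |
| 21-56 days | 1 − (11²/2)/(21 × 35) = 92% | (2²/2)/(21 × 35) = 0.3% |
| 28-84 days | (38 × 21 − 21²/2)/(21 × 56) = 49% | 0% (earliest sum 35) |

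If surgery is within 14 days of last dose and therapy starts within 14 days of surgery, the latest sum is 28, so both windows capture everything and there is no artefact. As an example at the other end, take the 21-56 day row with an assumed true rate of 70%. The table would show about 25.7/40 (64%) in each nivolumab arm and 0.1/30 (0.2%) in Arm C.

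**Step 4: when the gap shrinks or reverses.** Protocol 7.1.1 lets the oral drugs continue when a nivolumab dose is omitted. With oral drugs to Day 140:
- Last nivolumab at Cycle 4 Day 1 (Day 85): collection to Day 185, 15 days beyond Arm C.
- Last nivolumab at Cycle 3 Day 1 (Day 57): collection to Day 157, 13 days short of Arm C. FU1 would still apply to this participant, so for subsequent therapy the reversal follows the wording of Protocol 7.7 more than the visit schedule.

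**Step 5: general concomitant medication.** Assume a constant start rate r per day from first dose, so the percentage is 1 − exp(−r × days) over 213 or 170 days.

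| r | Arms A and B | Arm C |
|---|---|---|
| 0.005 | 66% | 57% |
| 0.01 | 88% | 82% |
| 0.02 | 99% | 97% |

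**Step 6: after the fix.** With one rule for all arms, collection counted in the table closes on Day 170 for every completer. The gap is 0, and equal true use gives equal expected percentages.

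**The case against.** The strongest reply is that little depends on these tables. The study is declared non-comparative. Subsequent therapy is not among the primary or secondary endpoints. No test, interval or decision rests on it, by-subject listings are planned, and the arm-specific windows are stated openly in SAP 7.4.3. All of that is correct and limits the weight of the point. It does not make the columns of an unlabelled percentage table comparable.

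Several stronger readings are tempting, but the documents do not support them:

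- **That the nivolumab arms will appear to need more therapy, or to respond worse.** Protocol 5.1 anticipates adjuvant treatment as ordinary care chosen by the treating physician. The table counts receipt, and the plan does not use it as a measure of response. The direction is also only a tendency, as Step 4 shows.
- **That most postoperative therapy in Arm C will go unrecorded.** This depends on start times that the documents do not give. If therapy starts within 14 days of surgery, Arm C captures about 76% under the assumptions of Step 3. The ±7-day allowance on FU1 could also move an Arm C visit to Day 177.
- **That the windows differ by 70 days (100 − 30).** They run from different events, so for completers the gap is 43 to 50 days.
- **That corticosteroid and other concomitant-drug rates are distorted to the same degree.** SAP 7.4.3.1 already sets a 30-day window for immune-modulating medication, apart from the tables on immune-mediated events, which use 100 days. Corticosteroids could still enter the general table, but the effect there is modest (Step 5).

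A fair objection to the remedy also stands: cutting every arm at 30 days discards most postoperative adjuvant therapy from the side-by-side table.

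**Conclusion.** The point holds for the subsequent-therapy table. Collection closes about 43 days later in Arms A and B than in Arm C for on-schedule completers, leaving 45-73 against 2-30 postoperative days, and SAP 7.4.3.2 does nothing to align them. Arms A and B would tend to show more participants receiving later therapy through collection time alone.

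The unequal windows and the 43 days follow from the documents. The size of the artefact does not: it ranges from none to near-complete loss in Arm C, depending on assumed surgery and adjuvant start times. The general concomitant-medication table shares the flaw to a modest degree. No endpoint, test or error rate is affected. The change should be made, as a matter of correct descriptive reporting.

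**What to change.** In SAP 7.4.3.2, and for consistency in 7.4.3:

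1. Base the side-by-side arm table on one window for all arms, from first dose to 30 days after last study treatment.
2. Show later data from Arms A and B and the run-in in a separate display, labelled as not collected in Arm C.
3. As an alternative to item 2, report cumulative incidence of subsequent therapy from surgery, censored at each participant's end of collection. For completers, Arm C then contributes at most 30 days after surgery (Step 2), so the arms can be set side by side only that far.

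The cost is SAP text and programming, with no new data or visits, because FU1 already covers all participants at 30 days. The downside is that the common-window table will contain little postoperative adjuvant therapy in any arm, and its title should say so.
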